7.2.6 Supplementary/sensitivity analyses

For all supplementary and sensitivity analyses of the primary endpoint analysis, the variable change from baseline in mSLEDAI-2K to Month 6 is derived as defined in Section 7.2.1 for the primary analysis.

7.2.6.1 Multiple imputation under MAR using mixed model for repeated measurements

This analysis will be conducted with multiple imputations in 3 steps using the FAS.

7.2.6.1.1 Step 1 (imputation)

Missing monthly mSLEDAI-2K scores will be imputed using a multiple imputation method [Rubin 1987], based on a model including the treatment group, the stratification factor OCS (from IXRS), the baseline mSLEDAI-2K score, and all post-baseline monthly scores up to Month 6.

Instead of imputing a single value for each missing observation, a set of values is generated from the model, resulting in as many distinct complete datasets without missing data.

More specifically, the imputations will be performed in two steps: ‘intermittent’ missing data (a monthly score is missing but one or more monthly score[s] is [are] available at following month[s]) will be first imputed by a Markov chain Monte Carlo method using a non-informative Jeffreys Prior, thus creating 100 partially imputed ‘monotone’ datasets, then the remaining missing data will be imputed once in each of these 100 ‘monotone’ imputed datasets using monotone regression leading finally to 100 complete imputed datasets. Imputed values will be restricted to remain in the clinically relevant range of [0, 104] but will not be rounded to integers.

The two-step multiple imputation procedure will be implemented by the following SAS[®] code:

```
proc mi data=h nimpute=100 seed=1234 minimum = . . 0 0 0 0 0 maximum = . . 104 104 104
104 104 104 minmaxiter=1000 out=h2;
  by trt;
  mcmc impute = monotone chain=single nbiter=200 niter=100;
  var ocs sledai_bl m1 -- m6;
run;

proc mi data=h2 nimpute=1 seed=1234 minimum = . . . 0 0 0 0 0 maximum = . . . 104 104 104
104 104 104 minmaxiter=1000 out=h3;
  by _imputation_;
  class treatment ocs;
  var treatment ocs sledai_bl m1 -- m6;
  monotone regression;
run;
```

In each imputed dataset, the change from baseline in mSLEDAI-2K from baseline to each monthly visit will be computed, as described for the primary endpoint. Imputed changes from baseline might not be integers.

7.2.6.1.2 Step 2 (analysis)

The analysis, within each imputed dataset, of the change in mSLEDAI-2K from baseline to Month 6 will be implemented by the following SAS[®] code:

```
proc mixed data=<data from step 1>;
class subjid ocs treatment month;
model change = ocs sledai_bl treatment month treatment*month sledai_bl*month / ddfm=kr;
repeated month / type = UN subject=subjid(treatment);

slice treatment*month / sliceby=month pdiff cl;
by _imputation_;
run;
```

7.2.6.1.3 Step 3 (combination)

Uncertainty in the imputations will be reflected appropriately in the analysis by combining the results on each imputed dataset into one summary measure. This method has been shown to be efficient in handling missing data if the missing data mechanism is missing completely at random or MAR [[Schafer 1999](#)].

The summary results across the 100 complete datasets will be aggregated following Rubin's rule. The final estimate is the mean of the 100 per-imputation estimates and the final variance is the sum of the average within-imputation variance and $(1+1/100)$ times the between-imputation variance [[Rubin 1987](#)]. From the final point estimate and variance, the 95% CI will be determined. The corresponding p-value will be displayed.

The results aggregation as the final step of the multiple imputation procedure after analysis of the 100 complete datasets will be implemented by the following SAS[®] code:

```
proc mianalyze parms= <data from step 2 >;
class treatment month;
modeleffect treatment*month;
run;
```

The robustness of this model will be assessed via several sensitivity analyses as described in the following sections.

7.2.6.2 Multiple imputation under MNAR using copy reference

This sensitivity analysis will be performed using the FAS.

The analysis of the primary endpoint described in Section 7.2.6.1 is based on the MAR assumption that “missingness” is independent of missing responses conditionally on observed responses.

The observed data cannot be used to distinguish between MAR and MNAR missing data mechanisms [NRC Report 2010] and in incomplete-data settings a definitive MNAR analysis does not exist [Molenberghs 2004]. However, a selected number of MNAR models can be used to check the robustness of the results to departures from the MAR assumption.

An analysis based on a pattern-mixture model will be performed keeping a ‘MAR imputation’ in the placebo arm while using an ‘MNAR approach’ in the cenerimod arm. This pattern-mixture model will follow the multiple imputation procedure described in Section 7.2.6.1.1 but with a modification in the second imputation step (after imputation of the ‘intermittent’ missing data). The remaining missing data in subjects from the cenerimod arm will be imputed based on data from the placebo arm, assuming that subjects from the cenerimod arm who stop providing data will exhibit the same future trajectories as subjects in the placebo arm, while the remaining data in subjects from the placebo arm will be imputed under the MAR assumption [O’Kelly 2014]. This imputation model using the available post-baseline data of each cenerimod subject to be imputed is following the copy reference approach [Carpenter 2013].

Step 1 will be implemented by the following SAS[®] code:

```
proc mi data=h nimpute=100 seed=6789 minimum = . . . 0 0 0 0 0 0 maximum = . . . 104 104
104 104 104 104 minmaxiter=1000 out=h2;
mcmc impute = monotone;
var treatment ocs sledai_bl m1 -- m6;
run;

proc mi data=h2 nimpute=1 seed=6789 minimum = . . 0 0 0 0 0 0 maximum = . . 104 104 104 104
104 104 minmaxiter=1000 out=h3;
by imputation ;
class treatment ocs;
var ocs sledai_bl m1 -- m6;
mnar model (m1 -- m6 / modelobs=(treatment="placebo"));
monotone regression;
run;
```

Steps 2 and 3 will be implemented as in Section 7.2.6.1.2 and 7.2.6.1.3.

7.2.6.3 Multiple imputation under MNAR using jump to reference

This sensitivity analysis will be performed using the FAS.

Steps 1 to 3 are repeated as described for the copy reference model in Section 7.2.6.2, with a code change in step 1, as displayed below. The jump to reference model is implemented by missing value imputations, separately for every visit, i.e., the imputation procedure will be repeated 6 times, once for each of the monthly visits.

```
proc mi data=h nimpute=100 seed=123 minimum = . . 0 0 0 0 0 maximum = . . 104 104 104 104
104 104 minmaxiter=1000 out=h2;
mcmc impute = monotone;
var ocs sledai_bl m1 -- m6;
run;

proc mi data=h2 nimpute=1 seed=123 minimum = . . 0 maximum = . . 104 minmaxiter=1000 out=m1;
by _imputation_;
class treatment ocs;
var ocs sledai_bl m1;
mnar model (m1 / modelobs=(treatment="placebo"));
monotone regression;
run;

proc mi data=m1 nimpute=1 seed=123 minimum = . . 0 maximum = . . 104 minmaxiter=1000 out=m2;
by _imputation_;
class treatment ocs;
var ocs sledai bl m2;
mnar model (m2 / modelobs=(treatment="placebo"));
monotone regression;
run;

...

proc mi data=m5 nimpute=1 seed=123 minimum = . . 0 maximum = . . 104 minmaxiter=1000 out=m6;
by _imputation_;
class ocs;
var ocs sledai_bl m6;
mnar model (m6 / modelobs=(treatment="placebo"));
monotone regression;
run;
```

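### The jump-to-reference code imputes dropouts in every arm from baseline and OCS stratum alone, which contradicts the MAR handling stated for placebo and lets arm-specific dropout move the result

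*SAP*

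**What the plan says.** SAP 7.2.6.3 builds on the copy-reference section: "Steps 1 to 3 are repeated as described for the copy reference model in Section 7.2.6.2, with a code change in step 1". The copy-reference section, 7.2.6.2, modifies only the cenerimod arms. For placebo it says that "the remaining data in subjects from the placebo arm will be imputed under the MAR assumption", and it describes MAR as missingness that does not depend on the missing responses once the observed responses are given.

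The code change in 7.2.6.3 has two stages.

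- The first call ("mcmc impute = monotone") fills intermittent gaps, with OCS, baseline and Months 1 to 6 all in the variable list.
- One call per visit follows: "The jump to reference model is implemented by missing value imputations, separately for every visit". The Month 1 call has "var ocs sledai_bl m1" and the Month 6 call has "var ocs sledai_bl m6". Month 2 is displayed in the same form and Months 3 to 5 are elided. Each call fits its model to placebo observations.

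The displayed Month 1 and Month 2 blocks declare both treatment and OCS as class variables. The Month 6 block declares OCS only, although it still selects on treatment.

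Elsewhere in the SAP, the second step of 7.2.6.1.1 (MAR) and the second step of 7.2.6.2 (copy reference) both keep Months 1 to 6 in the variable list.

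**The concern.** The text promises MAR for placebo given observed responses, and the code conditions on baseline and OCS only. A placebo subject who left while worsening receives a Month 6 value typical of placebo subjects who stayed, whatever scores that subject had at Months 1 to 5. The same happens to a cenerimod subject, whose own earlier scores are also set aside.

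Estimator #3 is one of two MNAR checks on the primary result in SAP Table 5. Such a check should move with the assumption it names. This one also moves with which arm loses its poor (or good) responders, so its result could be misread as robustness or as fragility.

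**Working it through.** **Text against code.** No arithmetic is needed here. SAP 7.2.6.2 defines MAR as conditional on observed responses. The Month 6 call in 7.2.6.3 contains no post-baseline month other than Month 6. For a placebo dropout the two cannot both hold, and 7.2.6.3 does not say that MAR is given up for placebo. Because Step 2 analyses completed data, the Month 6 call drives the Month 6 estimate.

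**Inputs from the documents.** 6% missing at Month 6 (SAP 7.2.3); 325 subjects in five equal arms (2.1), so 65 per arm and 0.06 × 65 = 3.9 missing per arm; target difference 1.5 (the Delta in the code of 7.2.6.9.5). The SAP gives no figure for this analysis, and no SD or correlation, so there is nothing to reproduce and these must be assumed.

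**Formula.** Let p_A and p_P be the Month 6 dropout proportions, and r_A and r_P the dropouts' mean Month 6 residuals (positive means worse than the arm average).

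- Intended jump to reference (placebo under MAR; cenerimod moved to the placebo mean, own residual kept): difference = −1.5 × (1 − p_A). At 6% this is −1.41, a penalty of 0.06 × 1.5 = 0.09, whatever the dropout mechanism.
- The code replaces each dropout's residual by the placebo completers' mean residual, c_P = −p_P r_P / (1 − p_P). The placebo mean shifts by c_P. The difference shifts from the intended value by −p_A r_A + (1 − p_A) p_P r_P / (1 − p_P).
- With equal dropout p this reduces to p × (r_P − r_A), which is zero if dropouts are alike in both arms.

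**SD 3.6, AR(1) 0.75.** With poor responders leaving, simulation moved the placebo mean by −0.10 at 6% dropout. So r = 0.10 × 0.94 / 0.06 = 1.57, and p × r = 0.06 × 1.57 = 0.094.

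- Poor responders leave cenerimod only: penalty 0.09 − 0.094, about 0.
- Poor responders leave placebo only: penalty 0.09 + 0.094, about 0.18.
- Both arms alike, or dropout unrelated to response: 0.09.

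**Wider range.** Simulation with 200,000 subjects per arm and a true difference of −1.5, in three settings: SD 3 with compound-symmetry correlation 0.7, SD 4 with AR(1) 0.7, and SD 3 with compound-symmetry correlation 0.5. Dropout is logistic in the last observed residual, with log-odds of 1.5 per SD (strong) or 0.5 (mild). Also assumed: placebo change −3, baseline SD 3, score bounds ignored. A negative penalty means that the estimate favours cenerimod more than MAR does.

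| Dropout (cenerimod / placebo) | Intended penalty | Penalty from the code |
|---|---|---|
| 6/6, unrelated to response | 0.09 | 0.09 |
| 6/6, poor responders, both arms | 0.09 | 0.09 |
| 6/6, poor responders, cenerimod only, mild | 0.09 | 0.03 to 0.05 |
| 6/6, poor responders, cenerimod only, strong | 0.09 | −0.08 to −0.03 |
| 6/6, poor responders, placebo only, strong | 0.09 | 0.21 to 0.25 |
| 9/3, poor responders, both arms | 0.135 | −0.015 to 0.024 |
| 3/9, poor responders, both arms | 0.045 | 0.16 to 0.21 |
| 15/15, poor responders, both arms | 0.225 | 0.225 to 0.228 |
| 20/10, poor responders, both arms | 0.30 | 0.09 to 0.15 |

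Check of the formula (SD 3, compound symmetry 0.7, strong): the placebo shift of −0.174 gives r = 0.174 × 0.94 / 0.06 = 2.73 and p × r = 0.164. The simulated net shifts are −1.573 + 1.408 = −0.165 (cenerimod only) and −1.247 + 1.410 = 0.163 (placebo only).

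**Unequal dropout, 12% and 6%** (SD 3.6, AR(1) 0.75). If poor responders leave, the intended analysis gives −1.32 and the code −1.41. If dropout is unrelated to response, they agree. If good responders leave, they give −1.30 and −1.21.

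**Repairing placebo alone.** With balanced poor-response dropout at 6%, placebo is no longer shifted, but cenerimod dropouts still receive the placebo completers' level. The shift is −0.06 × 1.57 − 0.06 × 0.10 = −0.10, and the penalty of 0.09 disappears. Simulation gave −1.49 against an intended −1.40.

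**The case against.** The strongest reply is that the visit-by-visit imputation is openly declared as the code change, and that the SAP gives no formula for jump to reference. A baseline-only jump is one way to read it for the cenerimod arms, and keeping each subject's own residual is a benchmark from outside the documents. That stands: for cenerimod the point is one of preference. It does not rescue placebo, where the SAP states MAR and the code does something else.

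The effect is also small. At 6% about 4 of 65 subjects per arm are concerned. Subjects who stop treatment remain in the study unless they withdraw consent (2.3.2), and their data are used (7.2.2). The primary MMRM and the copy-reference analysis do not share this fault. All of this stands, and it limits the point to one sensitivity analysis. The missing class variable at Month 6 looks like a slip, with no demonstrated effect on results.

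A reader might infer more than the documents support:

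- **That every missing visit is affected.** Only monotone (dropout) gaps are; intermittent gaps are filled by MCMC using Months 1 to 6.
- **That mis-imputing placebo is what weakens the penalty.** When poor responders leave, it makes placebo look better and adds penalty. The loss comes from the cenerimod arms.
- **That higher dropout on cenerimod alone makes the code lenient.** The 12%/6% results show no change, a loss or a gain, depending on who leaves.
- **That estimator #3 is meant as the stricter check.** Table 5 does not rank the estimators.

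**Conclusion.** The concern holds in a limited form. For monotone missing data, the code in 7.2.6.3 contradicts the MAR handling of placebo carried over from 7.2.6.2. That follows from the text and code alone.

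The consequence is conditional. The result of estimator #3 depends on response-related dropout that differs between arms as well as on the jump-to-reference assumption. At the expected 6% missing, strong differential selection moves the estimate by about 0.1 to 0.17 points in either direction, against a target difference of 1.5; mild selection on cenerimod moves it by about 0.04 to 0.06. Relative to an intended penalty of 0.09, that is enough to remove it or to double it or more. There is no effect when dropout is balanced or unrelated to response. The sizes rest on assumed SDs of 3 to 4, correlations of 0.5 to 0.75 and a logistic dropout model, none of which the documents give. The primary analysis is unaffected.

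**What to change.** Make three changes to step 1 of SAP 7.2.6.3, together:

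1. Impute placebo monotone missing values first, by monotone regression with the earlier months in the variable list, as in the second step of 7.2.6.1.1.
2. Impute cenerimod dropouts from the placebo mean profile after dropout. Estimate that profile from the MAR-completed placebo data or a joint placebo model, not from placebo completers only, and preferably keep each subject's own earlier residuals.
3. Add treatment to the CLASS statement of the Month 6 call.

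Items 1 and 2 belong together, because repairing placebo alone can remove the penalty. If the sponsor prefers the present code, the text should say that all arms, placebo included, are imputed from baseline and OCS only. That removes the contradiction but leaves the dependence on differential dropout.

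The cost is slightly more programming in one sensitivity analysis, with no change to data collection or design.

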7.2.6.4 Analyses based on PPS

The analysis of the primary endpoint as described in Section 7.2.5 will be conducted using the PPS.

7.2.6.5 Treatment effect over time

All monthly estimates related to the primary endpoint variable from the primary analysis model described in Section 7.2.5 will be reported as well.

Figures presenting the LSM differences versus placebo and their 95% CIs over time will be produced by treatment group using the FAS.

7.2.6.6 Complete case analysis

Only data from subjects with the complete information available at all visits from baseline to Month 6 will be included in the analysis of the primary endpoint as described in Section 7.2.5 (based on the FAS).

7.2.6.7 *Hypothetical estimand analysis*

This supplementary analysis does not use the treatment policy strategy to account for treatment discontinuation that is used for the primary analysis estimand, but rather, the hypothetical strategy. This means that all assessments collected after premature treatment discontinuation are not included in the analysis.

The analysis will be conducted in the same way as the primary analysis as described in Section 7.2.5 (based on the FAS).

7.2.6.8 *Analyses based on SLEDAI-2K*

7.2.6.8.1 *Variable*

The derivation of the ‘full’ SLEDAI-2K is based on the derived mSLEDAI-2K scores of the primary endpoint [see Section 7.2.1], including baseline and Month 1 to Month 6 scores, and the leukocyte value (from the central laboratory) at the corresponding visit.

If leukopenia is present at the corresponding visit the SLEDAI-2K score derives as:

$$\text{SLEDAI-2K at Visit X} = \text{mSLEDAI-2K at Visit X} + 1.$$

If leukopenia is not present or the leukocyte data are missing at the corresponding visit the SLEDAI-2K score is derived as:

$$\text{SLEDAI-2K at Visit X} = \text{mSLEDAI-2K at Visit X}.$$

Leukopenia is defined as a leukocyte value of $< 3000 \times 10^9/\text{L}$ (per visit).

7.2.6.8.2 *Analysis*

The analysis of the primary endpoint as described in Section 7.2.5 will be conducted on the SLEDAI-2K.

7.2.6.9 *Dose-response analysis*

7.2.6.9.1 *Dose-response analysis*

The objective of this supplementary analysis is to assess overall dose-response using modeling and multiple comparison procedures on the primary efficacy endpoint (change in mSLEDAI-2K from baseline to Month 6).

7.2.6.9.2 *Hypothesis and model*

The null hypothesis is that there is no dose response for the primary efficacy endpoint from baseline to Month 6, and the alternative hypothesis is the existence of a dose response:

$$H_0: p_d \geq p_{\text{placebo}} \text{ for all doses } d = 0.5, 1, 2, 4 \text{ mg}$$

vs

$$H_1: p_d < p_{\text{placebo}} \text{ for at least 1 dose } d = 0.5, 1.0, 2.0, 4.0 \text{ mg}$$

To meet the objective of defining a dose response on the reduction of mSLEDAI-2K from baseline to Month 6, the null hypotheses must be rejected with an exploratory one-sided significance level of 5%.

Dose-response data are analyzed using the MCP-Mod approach [Bretz 2005]. In brief, this methodology consists of three steps:

1. MCP step to establish a dose-response signal (i.e., the dose-response curve is not flat).
2. Mod step: Selecting the best dose-response model for the observed data out of a pre-specified set of candidate models, and
3. Mod step: Estimating target dose(s) of interest via modeling.

Five candidate models are considered: linear, linlog, E_{max} , sigmoidal E_{max} and logistic. See Table 6 for the parameterization of the dose-response models and Figure 3 as an illustration of their basic shapes. The initial values for the parameters are needed in the MCP step of the procedure. They will be estimated in the Mod step based on the actual data.

Table 6 Parameterization of models considered in MCP-Mod analyses

[figure not shown]
Model	Response*	Initial value(s) for parameters
Linear	$E_0 + \text{delta} \cdot \text{dose}$	NA*
Linear in log	$E_0 + \text{delta} \cdot \log(\text{dose} + 0.5)$	NA*
E_{max}	$E_0 + E_{max} \cdot \text{dose}/(\text{ED}_{50} + \text{dose})$	$\text{ED}_{50} = 1$
Sigmoidal E_{max}	$E_0 + E_{max} \cdot \text{dose}^h/(\text{ED}_{50}^h + \text{dose}^h)$	$\text{ED}_{50} = 1.5, h = 0.3$
Logistic	$E_0 + E_{max}/(1 + \exp[\{\text{ED}_{50} - \text{dose}\}/\text{delta}])$	$\text{ED}_{50} = 1.5, \text{delta} = 0.3$

Dose = 0, 0.5, 1, 2 and 4 mg of cenerimod;

*Not applicable for E_0 , delta (in linear and linlog models), and E_{max}

ED_{50} = dose giving half of the asymptotic maximum effect; E_{max} = maximum effect; linlog = linear in log; MCP-Mod = multiple comparison procedures - modeling; NA = not applicable.

Figure 3 Dose-response curves considered in MCP-Mod procedure

E_{\max} = maximum effect; linlog = linear in log; MCP-Mod = multiple comparison procedures - modeling.

Note that the ‘Model means’ on the vertical axis are plotted on a scale from 0 to -0.5 for illustrative purposes. The actual scale will depend on the endpoint analyzed.

The null hypothesis of ‘no dose response’ will be rejected if at least one of the five multiple contrast tests has a multiplicity adjusted p-value < 0.05 .

All statistically significant models (i.e., with a multiplicity adjusted p-value < 0.05) will be fitted in the Mod step and for each model AIC will be calculated. The smaller the value of AIC (= model deviance + 2 times the number of model parameters), the better the fit. The analysis will be performed using the R *DoseFinding* package [Bornkamp 2016].

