6.8.3.3.1 Variables

The mSLEDAI-2K relevant disease characteristics are recorded and derived from the data on the mSLEDAI-2K eCRF page at Visit 1 (Screening), and the variables include:

- Presence / no presence of each active descriptor
- Mucocutaneous score
- Musculoskeletal score
- Sum of the mucocutaneous and musculoskeletal score
- mSLEDAI-2K total score
- SLEDAI-2K total score
- mSLEDAI-2K total score as a category (≥ 10 and < 10)
- SLEDAI-2K total score as a category (≥ 10 and < 10)

mSLEDAI-2K

The SLEDAI-2K is a disease activity index of SLE based on the presence of 24 descriptors in 9 organ systems over the preceding 10 days.

Descriptors of the SLEDAI-2K are documented as either present or absent (or not done). Each of the descriptors is weighted and the total score of SLEDAI-2K is the sum of all

24 (weighted) descriptor scores. The range of the total SLEDAI-2K score is 0 to 105, with higher scores representing higher disease activity.

In this study, a modified SLEDAI-2K (mSLEDAI-2K) score is applied. The item related to leukopenia is excluded from the SLEDAI-2K scoring due to the mode of action of the compound (i.e., lymphocyte count reduction in peripheral blood). Therefore, the mSLEDAI-2K total score has only 23 descriptors and a maximum score of 104.

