7.2.3 Handling of missing data

Based on the Phase 2 study, AC-064A201, it is expected that 6% of subjects will have a missing mSLEDAI-2K result at Month 6.

Missing data will not be imputed but will be handled by the MMRM assuming that the data are MAR.

Various sensitivity analyses will be performed to evaluate the robustness of this assumption [see [Table 5](#)].

A summary of the patterns of missingness from baseline up to Month 6 will be provided as well as a figure presenting the mean change from baseline in mSLEDAI-2K for study completers and withdrawals by reason.

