8.4 Laboratory tests

Laboratory test results are transferred from the central laboratory or, if assayed locally, entered in local laboratory eCRF (in exceptional cases). Local laboratory data will only be listed (as local laboratory data is only requested in specific rare circumstances for medical evaluation of an individual subject).

Laboratory assessments are performed at each scheduled visit from Screening up to the EOS visit (except FU2, FU3, FU3a, and FU3b), and at unscheduled visits if required.

A time window approach will be applied to the laboratory data [as defined in Section 5.4.4].

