8.4.1 Measurements

The following parameters are assayed at any scheduled visit according to the protocol:

Hematology:

- Hemoglobin
- Hematocrit, mean corpuscular hemoglobin, mean corpuscular volume, and mean corpuscular hemoglobin concentration
- Erythrocyte count (reticulocyte count)
- Leukocyte count with differential counts (only available after database lock)
- Platelet count

Blood chemistry:

- Aspartate aminotransferase and alanine aminotransferase, alkaline phosphatase, total and direct bilirubin, lactate dehydrogenase
- Creatinine
- Blood urea nitrogen
- Uric acid
- Glucose
- Cholesterol, triglycerides
- Sodium, potassium, chloride, calcium
- Protein, albumin

Urinalysis (including but not limited to):

- pH

- Glucose
- Proteins
- Blood
- Leukocytes

Tests for tuberculosis, viral serology tests (Hepatitis B surface antigen, Hepatitis C antibodies, HIV1 and HIV2 antibodies, varicella-zoster virus IgG antibodies), coagulation tests (prothrombin time, international normalized ratio, activated partial thromboplastin time, urine-protein-to-creatinine ratio), other laboratory tests in the event of infection and pregnancy tests are also carried out during the study.

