8.4.3 Analysis

Laboratory parameters will be summarized using the SAF (for TP1 and for TP1+TP2 combined) and using the SAF-TP2 (for TP2) by visit and treatment group [as defined in Section 5.4.3]. Data will be displayed in SI units as provided by the central laboratory.

Treatment-emergent marked laboratory abnormalities (up to EOT + 180 days) as well as marked laboratory abnormalities during TP1 and during TP2 will be summarized by treatment group.

A subject will be counted only once in the most severe category of a given parameter. However, it is possible that, for a given parameter, the same subject is counted as a high marked abnormality for an observed value and as a low marked abnormality for a different

observed value. An abnormality is only counted as treatment-emergent if the criterion itself and all more severe criterion for the same parameter were not already present at baseline.

Percentages will be based on the number of subjects at risk, i.e., those not meeting the criterion or a more severe criterion for the same parameter at baseline (or having a missing baseline value) and having at least one post-baseline value for a given parameter. For criteria that are not only based on absolute values but also on changes from baseline, subjects with a missing baseline value are not included in the number of subjects at risk.

A standard laboratory listing will be produced using the SAF containing all central and local laboratory data collected in the database. Local laboratory data will only be listed.

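### The leukopenia cut-off in SAP 7.2.6.8.1 pairs a number and a unit that do not fit, so as written the SLEDAI-2K analysis cannot register leukopenia

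*SAP*

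**What the plan says.** The primary endpoint uses a modified score. SAP Section 6.8.3.3.1 explains why: "The item related to leukopenia is excluded from the SLEDAI-2K scoring due to the mode of action of the compound". The same section gives maxima of 105 for SLEDAI-2K and 104 for mSLEDAI-2K.

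Section 7.2.6.8 puts the item back for supplementary estimator #3 (Table 5), which reruns the primary MMRM on the full score. The derivation takes mSLEDAI-2K and "the leukocyte value (from the central laboratory) at the corresponding visit". It adds 1 if leukopenia is present. The zero-point branch covers two situations together: "If leukopenia is not present or the leukocyte data are missing at the corresponding visit the SLEDAI-2K score is derived as" equal to mSLEDAI-2K. Leukopenia is defined as "a leukocyte value of $< 3000 \times 10^9/\text{L}$ (per visit").

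On laboratory data, Section 8.4.3 states: "Data will be displayed in SI units as provided by the central laboratory". Section 8.4 says of local results: "Local laboratory data will only be listed". Neither the SAP nor the COVID-19 addendum (the public protocol document) gives another leukopenia threshold, and the SAP revision history records no change to Section 7.2.6.8.

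**The concern.** A limit of 3000 × 10^9/L lies far above any possible white-cell count, so it separates nobody. If the program follows the text and the counts arrive in 10^9/L, every subject with a central count is labelled leukopenic at every visit, before and after treatment.

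The item was dropped because the drug lowers circulating lymphocytes. Estimator #3 is where a reader would look to see what that choice did to the result. Under the printed limit it would agree almost perfectly with the primary analysis whatever the true leukopenia rates were. That agreement could be read as showing that dropping the item made no difference, when the question had not been tested.

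The slip may also surface late. Section 8.4.1 lists: "Leukocyte count with differential counts (only available after database lock"). A blinded dry run may therefore not show that every count is flagged, and a threshold changed after unblinding would look data-driven.

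**Working it through.** The SAP gives no derivation of the cut-off to reproduce, so the check starts from units.

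**Item weight.** 105 − 104 = 1 point, which agrees with the +1 rule.

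**Units.** One microlitre is 10^-6 L.
- 3000/µL = 3000 × 10^6/L = 3.0 × 10^9/L.
- Printed limit: 3000 × 10^9/L = 3 × 10^12/L = 3,000,000/µL.
- Ratio: 3000 / 3.0 = 1000.

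**Who is flagged.** The documents give no leukocyte range, so both limits were applied to an assumed grid from 0.1 to 500 × 10^9/L. Under the printed limit every value scores +1; even 500 is one sixth of 3000. Under 3.0 × 10^9/L, the grid values from 0.1 to 2.9 score +1 and those from 3.0 to 500 score 0.

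**Effect on the change score under the printed limit.** Let m_0 and m_X be mSLEDAI-2K at baseline and visit X.

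| Central counts available | Change in SLEDAI-2K | Difference from primary |
|---|---|---|
| Both | (m_X + 1) − (m_0 + 1) = m_X − m_0 | 0 |
| Baseline only | m_X − (m_0 + 1) | −1 |
| Visit X only | (m_X + 1) − m_0 | +1 |
| Neither | m_X − m_0 | 0 |

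With all counts present, the baseline covariate also rises by a constant 1. The month and baseline-by-month terms in the Section 7.2.5 model absorb this, so the treatment contrasts do not move. A numerical check on simulated data (5 arms of 65, Month 6 ANCOVA with baseline and OCS stratum) agreed: adding 1 to both scores changed treatment differences by at most 2.7e-15 and standard errors by at most 3.3e-16.

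**Size when counts are missing.** Section 2.1 plans about 325 subjects in five equal arms, and Section 7.2.3 says "it is expected that 6% of subjects will have a missing mSLEDAI-2K result at Month 6".
- Per arm: 325 / 5 = 65.
- Scored at Month 6: 65 × 0.94 ≈ 61.
- One missing count: 1/61 = 0.016 points in the raw arm mean, negative if the Month 6 count is missing and positive if the baseline count is.
- Three missing: 3/61 = 0.049. Six missing: 6/61 = 0.098.

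The 6% is used only to count scored subjects. The numbers of missing leukocyte counts are assumptions.

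In the simulated data, with all 65 per arm scored, missing Month 6 counts in 1, 3 and 6 subjects of one arm moved its difference from placebo by −0.015, −0.046 and −0.092. Missing baseline counts moved it by +0.015, +0.044 and +0.089. If missingness is balanced across arms, the shift in the treatment difference is about 0.

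**What a working cut-off would show.** With complete counts, each arm's raw mean change would differ from the primary by 1 × (proportion leukopenic at the visit − proportion leukopenic at baseline). The documents give neither proportion, so no size is claimed.

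**The case against.** The mismatch itself is hard to contest; the case against concerns its weight.

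- **It may be a reading error.** The text was extracted from a PDF, and 3000 × 10^6/L would be correct. This cannot be ruled out without the source file. But 10^9/L is the usual SI form for this count, and the visible extraction damage nearby consists of lost underscores, not altered digits.
- **The program may be right.** The printed limit does harm only if 3000 is compared with counts in 10^9/L. Code that uses 3.0, or 3000 on counts per µL, gives the intended result, and a 100% leukopenia rate would be conspicuous once counts are released. That is fair, but the SAP is the specification and should not depend on someone noticing.
- **The missing-count figures are hypothetical.** This stands. Baseline counts should rarely be missing, because hematology is scheduled at both Screening and Randomization. Addendum Section 2.2 also requires white-cell counts for subjects supplied at home, preferably through the central laboratory. Missing central counts after baseline remain plausible, since the addendum allows local analysis and local results are not used here.
- **Only a supplementary analysis is touched.** True, and it limits the severity.

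**Conclusion.** The concern holds. The cut-off as printed is wrong by a factor of 1000. Applied literally to counts in 10^9/L, it flags 100% of central counts, and estimator #3 then carries no leukopenia information. That conclusion needs only the assumption that no count reaches 3000 × 10^9/L.

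With complete counts the analysis duplicates the primary exactly. With incomplete counts the added point records whether a laboratory value exists. The resulting 0.05 to 0.10 points in a treatment difference rests on an assumed imbalance of 3 to 6 missing counts in one arm.

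The Hochberg families and the primary and secondary conclusions are untouched, and white-cell counts are still reported as safety data. The correction should be made because a pre-specified analysis fails its purpose as written and the repair is trivial.

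**What to change.** In SAP Section 7.2.6.8.1, state the limit as < 3.0 × 10^9/L (that is, < 3000/µL). Confirm it against the SLEDAI-2K scoring definition in the full protocol, which the public addendum does not contain. Check that the program uses that value in the unit of the central-laboratory transfer. The cost is one number and one program check. If results have already been seen, document the change as a correction of a unit error.

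Optionally, and separately, add a sensitivity run that sets SLEDAI-2K to missing when the central count is missing. This costs one extra output and discards some otherwise complete scores; a missing baseline count would remove the subject from that run.

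Local counts should not be substituted: the derivation specifies the central laboratory, Section 8.4 confines local data to listings, and Addendum Sections 2.1 and 2.2 ask for white-cell results to be redacted from local reports where that can be arranged.
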